**LIST OF ABBREVIATIONS**

Abbreviation	Description
AE	Adverse event
ANSI	American National Standards Institute
AQL	Acceptable Quality Level
ATC	Anatomical, Therapeutic, and Chemical
BMI	Body Mass Index
CDA	Clinical Data Associate
CI	Confidence interval
CRF	Case report form
CVC	Central venous catheter
DMC	Data Monitoring Committee
eCRF	Electronic case report form
ET	Early termination
GCP	Good Clinical Practice
HAV	Human acellular vessel (Note: was HAVG [Human Acellular Vascular Graft])
HbA1c	Hemoglobin A1c
ICH	International Conference on Harmonization
IEC	Independent ethics committee
IgG	Immunoglobulin G
IMP	Investigational medicinal product
INR	International normalized ratio
ITT	Intent-to-Treat
K-M	Kaplan Meier
MedDRA	Medical Dictionary for Regulatory Activities
PI	Principal Investigator
PP	Per-Protocol
PRA	Panel reactive antibody
PT	Preferred Term
QC	Quality Control
RDC	Remote data capture
SAE	Serious adverse event
SAP	Statistical Analysis Plan
SOC	System Organ Class
SOP	Standard operating procedure
TEAE	Treatment-emergent adverse event
TESAE	Treatment-emergent serious adverse event
WHO	World Health Organization

## 1. INTRODUCTION

This statistical analysis plan (SAP) is based on Humacyte Inc.'s Protocol # CLN-PRO-V011, titled "A Phase 2 Assessment of Humacyte's Human Acellular Vessel in Patients Needing Vascular Access for Dialysis". See the study Protocol for details on study rationale, conduct and endpoints.

The purpose of this SAP is to provide details of the statistical analyses specified in the study protocol. The SAP summarizes key aspects of the study to provide context for statistical methods and presents details of the planned statistical methods addressing:

- The primary analysis after the last subject completes 3 months of follow up,
- A second analysis after all subjects have completed 12 months of follow up, and
- A final analysis of the study after the final subject completes 36 months follow up.

This study will be conducted in compliance with the study protocol and ICH guideline E9  ([Statistical Principles for Clinical Trials 1998](#)).

## 2. OBJECTIVES AND ENDPOINTS

### 2.1 Objectives

#### 2.1.1 Primary Objective

To evaluate the safety, efficacy and immunogenicity over 3 months after implantation of HAVs manufactured using the commercial manufacturing system (LUNA).

#### 2.1.2 Secondary Objectives

To evaluate the long-term safety and efficacy of the HAV (manufactured with the LUNA system) over a period of up to 36 months after implantation.

### 2.2 Endpoints

#### 2.2.1 Primary Endpoints

##### 2.2.1.1 Primary Safety Endpoints – assessed at 3 months post implantation

- Adverse events indicating possible mechanical failure or weakness of the HAV
  - Anastomotic rupture
  - Anastomotic bleeding
  - Spontaneous HAV rupture
  - Aneurysm
  - Pseudoaneurysm
  - Abnormal post cannulation hemostasis
- HAV infections
- Change from baseline of panel reactive antibody (PRA) and anti-HAV IgG levels (at 2

months)

- All adverse events (AEs)/serious adverse events (SAEs) and adverse events of special interest

### **2.2.1.2 Primary Efficacy Endpoints – assessed at 3 months post implantation**

- Primary patency
  - Defined as being maintained until any intervention designed to maintain or reestablish patency, access thrombosis or the measurement of patency', i.e., patent without interventions
- Primary assisted patency
  - Defined as being maintained until access thrombosis or the time of measurement of patency, including intervening manipulations (surgical or endovascular interventions) designed to maintain the functionality of patent access' i.e., patent without an intervention to clear a thrombus
- Secondary patency
  - Defined as being maintained until access abandonment
  - Access abandonment defined as no remaining segment of the study conduit is incorporated into the vascular access circuit used for dialysis

## **2.2.2 Secondary Endpoints**

### **2.2.2.1 Secondary Safety Endpoints – assessed throughout the 36 months post implantation follow-up**

- Adverse events indicating possible mechanical failure or weakness of the HAV
  - Anastomotic rupture
  - Anastomotic bleeding
  - Spontaneous HAV rupture
  - Aneurysm
  - Pseudoaneurysm
  - Abnormal post cannulation hemostasis
- HAV infections
- Change from baseline of PRA and anti-HAV IgG levels (at 12 months)
- All AEs/SAEs until 12 months post implant, after that only SAEs associated with the HAV and adverse events of special interest.

### **2.2.2.2 Secondary Efficacy Endpoints – assessed throughout the 36 months post implantation follow-up**

- Primary patency

- Primary assisted patency
- Secondary patency
- Interventions required to achieve/maintain secondary patency
- Histopathological remodeling of any HAV (based on any samples collected)

### **3. INVESTIGATIONAL PLAN**

#### **3.1 Study Design**

This is a Phase 2, prospective, multicenter, open-label, single-arm study. Previous studies with the HAV have used Investigational Medicinal Product (IMP) manufactured using small-scale systems (Aura and Terra). Prior to commercialization, manufacturing has been switched to a larger-scale automated process with greater in-process controls (LUNA). Based on a large number of preclinical parameters, including those used for batch release, the IMP manufactured using the LUNA system is comparable to that used in earlier clinical studies. This study will allow confirmation of the short-term safety, efficacy and absence of immunogenicity of the LUNA product.

Up to 30 subjects who meet the inclusion/exclusion criteria specified in the Protocol, Section 5.1 will receive a HAV and will be followed to 12 months post-implantation at routine study visits regardless of patency status. After 12 months, subjects with a patent HAV will be followed (while the HAV remains patent) for up to 3 years (36 months) post-implantation at study visits every 6 months. See Appendix A for visit schedule.

#### **3.2 Treatment**

##### **3.2.1 Randomization Scheme and Treatment Arm Assignment**

This is a single-arm, open-label study. No randomization scheme or treatment arm assignment applies.

##### **3.2.2 Blinding**

This is an open-label study. Blinding of study subjects or study staff does not apply.

##### **3.2.3 Dosing Schedule**

The Humacyte HAV is a tissue-engineered vascular conduit for hemodialysis access. HAVs for this study will be manufactured using the LUNA commercial manufacturing system. Subjects will be implanted with an HAV in the forearm or upper arm using standard vascular surgical techniques on Day 1.

##### **3.2.4 Subject Compliance with IMP**

Not Applicable; the HAV is surgically implanted and remains *in situ* unless, in the judgment of the investigator, part or all of it requires explantation.

#### **4. GENERAL CONSIDERATIONS FOR DATA ANALYSIS**

CTI Clinical Trial and Consulting Services will perform all efficacy and safety statistical analyses described in this SAP. Any change to the data analysis methods described in the protocol will require an amendment of this SAP only if it changes a principal feature of the protocol. Any other change to the data analysis methods that are described in the protocol, and the justification for making the change, will be described in the clinical study report. Additional exploratory analyses of the data will be conducted as deemed appropriate.

The analyses for this study will be performed as follows:

- The primary analysis will be performed after the last subject completes 3 months of follow-up.
- A second analysis will be performed after all subjects have completed 12 months of follow-up.
- A final analysis will be performed after the last subject completes 36 months of follow-up.
- Interim safety data will be provided periodically to the Data Monitoring Committed (DMC) as per the DMC Charter.

A soft database lock will be required for the data included in the planned primary (3 months) and second (12 months) analyses. A final hard lock will be required for the final analysis at 36 months.

Statistical analyses will be primarily descriptive in nature. Unless otherwise specified, continuous variables will be summarized by presenting the number of non-missing observations, mean, standard deviation, median, inter-quartile range, minimum and maximum. Categorical variables will be summarized by presenting the number of subjects and percentage for each category.

All tabulations will be based on pooled data across centers.

Analyses will be performed using SAS for Windows statistical software, version 9.4 or higher (SAS, Cary, NC), except where other software may be deemed more appropriate.

Subject data will be listed and sorted by subject number.

##### **4.1 Data Quality Assurance**

It is the responsibility of Humacyte or designee to perform auditing (if applicable) as part of implementing quality assurance. The purpose of an audit, which is independent of and separate from routine monitoring or quality control functions, is to evaluate trial conduct and compliance with the protocol, SOPs, GCPs, and the applicable regulatory requirements. Authorized representatives from Humacyte, regulatory authorities and IEC will be granted access to the site and relevant study documentation to perform audits or inspections. The Principal Investigator (PI) should contact Humacyte immediately if contacted by a regulatory agency about an inspection involving this protocol.

A study coordinator at the study site will enter subject data into a remote data capture (RDC) database by completing eCRFs. All information recorded in the eCRFs for this study must be consistent with the investigator's source documentation for the study subjects. The study site will make available source documents to CTI personnel monitoring the study. The study monitor will verify consent of all subjects to participate in the study and will perform 100% source document

*Humacyte CLN-PRO-V011 Statistical Analysis Plan v1.0*

verification of the eCRF data.

A CTI Clinical Data Associate (CDA) will review the data for discrepancies via programmed electronic consistency checks, data listings, or manually. Any discrepancies discovered via the data review process will be issued as queries in the RDC system to the study site for resolution. Once all the source verification is complete, all queries are resolved, and the database has been updated appropriately, the database will be locked/frozen and made available to CTI Biostatistics for 3 months, 12 months, and final analyses.

Data may be pulled by CTI Biostatistics for analyses of DMC meetings at a time when source verification and query resolution is ongoing.

All SAS programs used to create analysis datasets and output will be validated by ensuring that the “.log” files are void of all errors, warnings and notes indicative of problems. Additionally, each program will be checked to ensure that it performs according to the program specification. All programs are developed and validated by separate members of the CTI Biostatistics Department.

At the time of analysis, a quality control (QC) review of database values listed in SAS output will be compared to the database. The sample size of fields to undergo QC review will be determined by utilizing American National Standards Institute (ANSI) sampling procedures . Sampling procedures are conducted using “normal” inspection criteria (Inspection Level II, Single, and Normal) and an Acceptable Quality Level (AQL) of 0.010%. The following shows the sampling criteria:

**Single Normal sampling procedure for Acceptable Quality Level (AQL) 0.010%**

Number of Fields	Sample Size	Accept/Reject Criteria
2-8	2	0/1
9-15	3	0/1
16-25	5	0/1
26-50	8	0/1
51-90	13	0/1
91-150	20	0/1
151-280	32	0/1
281-500	50	0/1
501-1,200	80	0/1
1,201-3,200	125	0/1
3,201-10,000	200	0/1
10,001-35,000	315	0/1
35,001-150,000	500	0/1
150,001-500,000	800	0/1
500,001-up	1,250	0/1

## 4.2 Analysis Sets

The following three analysis sets will be defined for this study:

- **Intent-to-Treat (ITT) set:** The ITT set will include all enrolled subjects. The efficacy analysis will be based on the ITT set.
- **Per Protocol (PP) set:** The PP set is defined as all enrolled subjects in whom a HAV has been implanted and in whom there were no major protocol violations. Major protocol violations which would exclude a subject from the PP set will be defined by the sponsor prior to the database lock. Any protocol violation arising during the study which might have a substantial impact on the evaluation of efficacy or safety of HAV and which was not pre-specified as major, will be reviewed by Humacyte who will decide if the subject should be excluded from the PP set. If the number of subjects in the ITT set is different from that in the PP set, efficacy analysis on HAV patency will be repeated in the PP set.
- **Safety analysis set:** The Safety analysis set will include all enrolled subjects in whom a HAV has been implanted. The safety analysis will be conducted in the Safety analysis set.

## 4.3 Assessment Windows

For the purpose of listing and summarizing data, the time-in-study for each subject observation will be defined using study days. Such days will be calculated as follows:

- Date of assessment – date of HAV implantation + 1 for assessments done on or after date of HAV implantation
- Date of assessment – date of HAV implantation for assessments done before date of HAV implantation

Data will be summarized based on the eCRF study visit in which it was collected.

Baseline is defined as the last non-missing value prior to the HAV implantation.

If a repeat laboratory sample was drawn for a visit, the values from the repeat sample will be used for summary and analysis purposes. In this case, only the repeat sample values will be listed.

## 4.4 Handling of Dropouts or Missing Data

### 4.4.1 Time-to-Event Analyses

The following censoring rules will apply to all “time to event” analyses:

- Subjects who have patent HAV at the time of death, kidney transplant or withdrawal will be censored at that timepoint.
- Subjects who are lost to follow-up with a patent HAV will be censored at their last known visit.
- Subjects lost to follow up whose HAV was not patent at the last completed visit will be treated as abandoned at the time of HAV occlusion and recorded in the eCRFs.
- Subjects in whom a delayed decision is made to abandon the HAV (e.g. delayed and then failed thrombectomy) will have the date of abandonment recorded as the date of the initial recognition of the thrombosis, not the date that a final decision is made.

## *Humacyte CLN-PRO-V011 Statistical Analysis Plan v1.0*

- For subjects who discontinue early or who complete without meeting criteria for the event, the time-to-event will be censored at the subject's last date of study participation recorded in the eCRF disposition form.

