### **4.4.2 Missing Data**

No substitution of missing data will be used in laboratory measurements, vital signs, physical examinations and subject and graft status.

In case of partially missing adverse event start dates, the start dates will be imputed by comparing to the implantation date of HAV so that the corresponding AEs will be made treatment-emergent whenever possible, unless the available partial date information clearly indicates that the event happened before implantation. The general rule of imputation is to assign the first day of a month for a missing day and the first month of a year for a missing month when applicable.

For interventions, if the date of a procedure has a missing day, the first day of that month will be assigned for the missing day unless the partial date has the same year and month as the implantation date, in which case, the day of the implantation will be assigned.

For a partially missing initial renal replacement therapy date, the last day of the month will be assigned for the missing day and no imputation will be performed if both month and day are missing.

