### **6. EFFICACY ANALYSES**

The status of Primary Patency, Primary Assisted Patency, and Secondary Patency will be assessed by the PI at Month 3, Month 12, and the end of the study. The patency status and the date of loss of patency will be recorded in the eCRF and used for the time-to-event analysis.

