## *Humacyte CLN-PRO-V011 Statistical Analysis Plan v1.0*

The time to loss of Primary/Primary Assisted/Secondary patency will be analyzed by K-M method as described in Section 6.1. The K-M estimates of the proportion of subjects event-free at 6, 12, 24, and 36 months will be provided.

Interventions include whatever is done at one session. For example, thrombectomy + angioplasty at one session would be considered as one intervention. Summaries for interventions required that successfully achieved/maintained Secondary Patency will include:

- Number of interventions per subject
- Rate of interventions defined as the number of interventions per subject per year while the HAV is patent (i.e. has not been abandoned). Results will be provided for Day 0 to Month 12 and overall (Day 0 to total follow-up period).
- The number and percent of subjects with each of reasons for interventions
- The number and distribution of thrombectomies, angioplasties, stents, etc. will be analyzed separately

Analysis of histopathological remodeling of HAV will be performed by Humacyte.

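### SAP 4.4.1 counts an occluded HAV as abandoned only for subjects lost to follow-up, so a withdrawal or occlusion-driven exit with no recorded abandonment can be censored event-free for secondary patency (a narrow gap, minor)

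*SAP*

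**What the plan says.** The secondary patency event is abandonment, not occlusion. SAP 2.2.1.2 defines abandonment as the state in which "no remaining segment of the study conduit is incorporated into the vascular access circuit used for dialysis". SAP 4.4.1 then gives one set of rules for all time-to-event analyses:

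- Death, transplant, withdrawal: "Subjects who have patent HAV at the time of death, kidney transplant or withdrawal will be censored at that timepoint".
- Lost to follow-up with a patent HAV: censored at the last known visit.
- Lost to follow-up with a non-patent HAV: "Subjects lost to follow up whose HAV was not patent at the last completed visit will be treated as abandoned", dated to the occlusion.
- Delayed decision to abandon: backdated to the first recognition of thrombosis.
- Everyone else: "For subjects who discontinue early or who complete without meeting criteria for the event, the time-to-event will be censored", at the last date of participation.

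Under SAP 3.1, all subjects are followed to Month 12 whatever the patency status. After that, "subjects with a patent HAV will be followed (while the HAV remains patent) for up to 3 years". SAP 6 takes patency status and date of loss from the investigator's eCRF entries: "Secondary Patency will be assessed by the PI at Month 3, Month 12, and the end of the study".

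**The concern.** The third rule shows that the SAP regards an unrestored occlusion at exit as a failure. It applies that view to one exit type only. A subject with the same vessel status who is coded as withdrawn, or whose follow-up stops because the HAV is occluded, is not named by any specific rule. Unless abandonment has been recorded, such a subject falls to the closing rule and leaves the risk set without an event.

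That censoring would be informative, because the subject leaves with a vessel that has stopped working. After Month 12 the occlusion may itself be the reason for leaving. Secondary patency is a primary efficacy endpoint at 3 months and a secondary endpoint through 36 months, so its event status should not turn on a disposition code. Primary and primary assisted patency are not affected, because thrombosis already ends both.

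**Working it through.** **Step 1: the rules applied to a subject whose HAV is occluded and not restored, with no recorded abandonment.**

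| Exit | Rule in SAP 4.4.1 that applies | Result |
|---|---|---|
| Lost to follow-up | Third rule | Event at occlusion |
| Withdrawal | First rule does not apply (HAV not patent); closing rule does | Can be censored |
| Follow-up ends after Month 12 because the HAV is occluded | None specific; closing rule | Can be censored |

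The delayed-decision rule does not help here, since it needs a decision to abandon.

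**Step 2: the two senses of patent.** In the third rule of 4.4.1, not patent goes with occlusion. In SAP 6.2 the intervention rate runs "while the HAV is patent (i.e. has not been abandoned", so patent there means not abandoned. If SAP 3.1 uses the 6.2 sense, follow-up after Month 12 ends at abandonment, which is the event, and the last row of the table disappears. If it uses the 4.4.1 sense, occlusion alone can end follow-up. The SAP does not say which applies.

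**Step 3: size per case.** The plan gives no figure for this, so there is none to reproduce. The size is illustrated with the Kaplan-Meier estimator, S(t) = product over event times of (1 − d/n), where d is the number of events and n the number at risk. Each case is coded either as an event at occlusion or as censored 0.3 month later.

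Inputs: n = 30, the planned maximum (Protocol Summary). The background is assumed: seven abandonments at months 4, 8, 11, 14, 17, 20 and 22. It gives 29/30 = 96.7%, 27/30 = 90.0% and 23/30 = 76.7% at Months 6, 12 and 24, close to the 97%, 91% and 77% that Protocol 2.3.2.1 reports for the earlier dialysis studies. Deaths with a patent HAV are assumed to be 0, 2 (months 6.5 and 10.5) or 4 (also months 15.5 and 19.5).

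Month 3, no other events: censored 100.0%; counted 29/30 = 96.7%, a difference of 3.3 points. At n = 25 it is 1/25 = 4.0 points and at n = 20 it is 1/20 = 5.0.

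Worked example at Month 24, occlusion at month 17.5, no deaths:

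- Counted: eight events in 30, 22/30 = 73.3%.
- Censored: 25/30 after five events, then 24 at risk at month 20 and 23 at month 22, so 25/30 × 23/24 × 22/23 = 76.4%.

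| Estimate at | Occlusion (month) | Deaths | Censored | Counted | Difference (points, from unrounded values) |
|---|---|---|---|---|---|
| Month 12 | 5 | 0 | 89.8% | 86.7% | 3.1 |
| Month 12 | 8.5 | 2 | 89.5% | 86.2% | 3.3 |
| Month 24 | 11.6 | 0 | 76.2% | 73.3% | 2.8 |
| Month 24 | 17.5 | 0 | 76.4% | 73.3% | 3.1 |
| Month 24 | 17.5 | 4 | 74.1% | 70.7% | 3.4 |
| Month 24 | 23 | 4 | 74.5% | 70.5% | 3.9 |

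With a lighter background (abandonments at months 4, 8 and 11, deaths at months 6 and 10), one case at month 17 gives 89.6% against 86.0%, or 3.6 points. For scale, the 95% interval around 73.3% (Greenwood variance, log-log) runs from 53.7% to 85.7%.

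**The case against.** The strongest reply is that the event definition already closes most of the gap. Every subject is on hemodialysis at entry (Protocol 5.1.1), so one whose HAV is occluded and not restored must be dialysed another way, and that route is recorded at each visit. The conduit is then arguably out of the access circuit, the abandonment criterion is met, and the closing rule does not apply.

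Recording is also strong. HAV thrombosis and events leading to abandonment are Events of Special Interest (Protocol 9.3), with notes on the outcome of any intervention or abandonment due within 48 hours (Protocol 8.3.8). SAP 4.1 requires full source verification and resolution of queries before lock. Most of this stands, and it is why the point is minor. It does not remove the gap: the SAP nowhere says that an occlusion with no decision counts as abandonment, and if that were always understood, the third rule would be unnecessary.

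The earlier peripheral arterial study cuts both ways. Protocol 2.3.3.1 reports four of 20 patients withdrawn after occlusion, so this kind of exit does occur. The reported 24-month secondary patency of 73.7% equals 14/19, which fits those four having been counted as failures. That is an inference from another indication, and its rate does not carry over.

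Three stronger readings are tempting, and the documents do not support them:

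- **The 3-month result is at material risk.** Before Month 12, occlusion cannot end follow-up by design. A case at Month 3 needs a voluntary withdrawal with an occluded HAV and no recorded loss, so there may be none.
- **SAP 4.4.2 forces the censoring.** It says "No substitution of missing data will be used in laboratory measurements, vital signs, physical examinations and subject and graft status". That concerns missing status, and a recorded occlusion is not missing.
- **Completion, death and transplant with an occluded HAV are handled wrongly too.** Secondary patency lasts until abandonment, so a salvageable HAV occluded at Month 36 need not be a failure. For death or transplant, the choice is a matter of judgement.

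**Conclusion.** The concern holds in a limited form. SAP 4.4.1 allows the same vessel status at exit to be an event for a subject lost to follow-up and a censoring for one who withdraws, or whose follow-up ends after Month 12 because of the occlusion, when no abandonment is recorded. It matters most after Month 12.

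At n = 30 each case is worth about 3 to 4 points of estimated secondary patency, upward only relative to counting the case. This rests on the assumed event and exit times above. The number of cases is unknown. Protocol 2.3.2.1 says that thrombosis was nearly always managed successfully in the earlier dialysis studies, which suggests few. The study is descriptive, and one case is small beside the interval. Severity: minor.

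**What to change.** In SAP 4.4.1, extend the lost-to-follow-up rule to withdrawal and to end of follow-up because the HAV is not patent: an HAV recorded as occluded and not restored at the last assessment counts as abandoned at the date of occlusion. State that this takes precedence over the closing rule, and that it applies at exit only, not to subjects still in follow-up at a data cut. Use patent in one sense in 4.4.1 and 6.2.

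Report how many subjects the rule affects, with a sensitivity Kaplan-Meier estimate in which they are censored. Leave subjects who complete Month 36 under the abandonment definition in SAP 2.2.1.2. For death or transplant with an occluded HAV, report the number and no more.

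The cost is SAP wording, one derived flag and one extra estimate. No new data are needed: patency status and date of loss are already in the eCRF (SAP 6), and the early termination visit covers patency, ultrasound and the reason for abandonment (Protocol 8.7). The downside is that estimated secondary patency may be slightly lower, and a few salvageable occlusions may count as failures.
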